1 BACKGROUND

1.1 Fabry disease

Fabry disease (FD) is a rare, pan-ethnic X-linked inherited glycosphingolipid (GSL) storage disorder caused by the deficiency of the lysosomal enzyme α -galactosidase A (α -GalA) [Germain 2010]. In FD, mutations in the gene coding for α -GalA (*GLA* gene), located on the X chromosome, are responsible for reduced expression and/or activity of α -GalA resulting in accumulation of globotriaosylceramide (Gb3), globotriaosylsphingosine (lysoGb3), and other neutral GSLs in lysosomes and other subcellular compartments. Progressive storage of these GSL molecules eventually leads to cellular dysfunction, associated with inflammation and/or fibrosis which results in multisystem disease, mainly affecting the kidneys, heart, and nervous system.

Diagnosis of FD combines clinical presentation, α -GalA activity and *GLA* mutations, as defined in the most recent international guidelines [Schiffmann 2017].

There are 2 major phenotypes: a classic phenotype and a late-onset (also referred to as “atypical” or “non-classical”) phenotype [Arends 2017].

The classic phenotype is more severe due to little or no α -GalA activity. The first clinical symptoms (e.g., neuropathic pain, gastrointestinal [GI] symptoms, abnormal sweating) interfering with well-being and daily activities arise in childhood [Hopkin 2008]. In the absence of treatment, progressive damage to vital organ systems occurs in subjects with FD over several decades, resulting in end-stage renal disease and/or life-threatening cardiovascular or cerebrovascular complications, causing substantial morbidity, significantly impaired quality of life (QoL), and premature death [MacDermot 2001a, MacDermot 2001b].

The late-onset phenotype is typically less severe and is observed in subjects with significant residual α -GalA activity. It is characterized by a more variable disease course, and disease manifestations may be limited to a single organ, e.g., the heart.

As expected for an X-linked disorder, males with deleterious mutations have little or no residual α -GalA activity. Therefore, these male subjects usually experience the full spectrum of disease symptoms. In heterozygous female subjects with FD (carriers) who have a mutation in one copy of the *GLA* gene, random X inactivation effectively results in mosaic expression, with some cells exhibiting normal α -GalA activity and others with little or no α -GalA activity [Linhart 2007]. The severity of the disease is heterogeneous in female carriers, who, like male subjects and somehow unexpectedly, may develop life-threatening complications of the disorder. Up to 70% of female carriers develop FD-related symptoms, including neuropathic pain, GI symptoms, renal and cardiac disease,

and/or stroke [Schiffmann 2009]. In general, affected female carriers experience symptoms similar to hemizygous males with a delayed onset and slower progression compared to men [Linhart 2007].

1.1.1 Current treatment of Fabry disease

The management of FD consists of conventional palliative management, enzyme replacement therapy (ERT), and chaperone therapy.

Conventional management consists of pain medications, angiotensin-converting enzyme (ACE) inhibitors or angiotensin receptor blockers (ARBs) to protect the heart and kidney, antiarrhythmic agents, and anticoagulants to avoid thrombotic complications. Dialysis or renal transplantation are available for subjects experiencing end-stage renal failure. A recent review of the pharmacotherapy for neuropathic pain in Fabry adult subjects recommends using anti-epileptics (e.g., carbamazepine, gabapentin), tricyclic antidepressants (TCAs; e.g., amitriptyline), and other antidepressants of the serotonin-norepinephrine re-uptake inhibitor class (SNRIs; e.g., duloxetine, venlafaxine) as first-line therapy [Finnerup 2015, Politei 2016]. Non-opioid and opioid analgesic drugs are used as second- and third-line treatments, respectively. Due to the limited evidence with respect to the effectiveness of pain medication in FD, clinicians usually rely on local clinical experience or follow national and international guidelines for the management of neuropathic pain [Finnerup 2015].

Two injectable ERTs have been granted market authorization in at least 1 country for the treatment of FD: agalsidase alfa (Replagal[®]) and agalsidase beta (Fabrazyme[®]). However, their effectiveness in controlling all symptoms and complications of FD is limited (see below). Chaperone therapy is also available to improve the activity of some defective enzymes. In FD, migalastat (Galafold[®]), an oral small molecule pharmacological chaperone, has been granted market authorization in at least 1 country for the treatment of subjects with amenable mutations.

The most recent international guidelines provide the framework for screening, diagnosis and management of patients with FD [Biegstraaten 2015, Schiffmann 2017]. They include recommendations on the use of ERT, the discontinuation of ERT, the monitoring of Fabry-specific symptoms and organ diseases, and the use of adjunctive therapy. Recommendations for diagnosis and management of neuropathic pain in subjects with FD are also available [Politei 2016].

1.1.2 Unmet medical need in Fabry disease

Despite ERT administration, a large proportion of subjects with FD still exhibit clinical symptoms, in particular neuropathic pain, which impact their daily life. Although an effect on neuropathic pain after 6 months of treatment with agalsidase alfa has been suggested in a placebo-controlled study [Schiffmann 2001], the totality of the data provided no clear

evidence that ERT treatment is associated with improvement in the “worst pain” Brief Pain Inventory (BPI) scores. While no other placebo-controlled study was performed to assess the effect of ERT on neuropathic pain, further data from the Fabry Outcome Survey (FOS) registry [Hoffmann 2005] and a comparative trial with agalsidase alfa or beta [Vedder 2007] showed little or no improvement in neuropathic pain with ERT in subjects with FD.

The effects of ERT on different organs/systems in subjects with FD have been extensively evaluated [Eng 2001, Banikazemi 2007, Schiffmann 2001]. Overall, some limited improvements in renal function, cardiac mass, cerebrovascular complications, and QoL have been reported [Mehta 2009]. Long-term effects of ERT on risk of morbidity and mortality related to FD remain to be established even to this day [El Dib 2016].

ERT for FD has intrinsic limitations such as a very short half-life combined with a low tissue penetration, in particular in the nervous system [Murray 2007, Thurberg 2004, Thurberg 2009], and the development of antibodies to the infused protein in many subjects [Deegan 2012]. Inhibitory antibodies may compromise the efficacy of the treatment with ERT [Lenders 2016]. Furthermore, the intravenous (i.v.) route of administration for ERT is associated with an elevated risk of adverse events (AEs) and it can be inconvenient [Mehta 2009].

The oral administration of migalastat is restricted to subjects with amenable mutations only, which represent approximately 30% of all known *GLA* mutations [Galafold® SmPC]. In that population, the Phase 3 study results suggest that migalastat may provide some beneficial clinical effects, e.g., stabilizing renal function and decreasing left ventricular mass index (LVMI) [Germain 2016]. However, long-term data with the use of chaperone therapy in FD is tenuous.

Overall, there is still an unmet medical need in the treatment of subjects with FD. The available therapies have not yet demonstrated long-term clinical benefit on the main symptoms such as neuropathic pain. In addition, their use is either restricted due to their mode of administration (i.v. infusion) and immunogenic potential or indicated only in a subset of subjects with FD.

1.2 Lucerastat

1.2.1 Mechanism of action

Lucerastat is an iminosugar that has the potential to provide substrate reduction therapy (SRT) for the treatment of FD. The goal of SRT with lucerastat in FD is to inhibit the enzyme glucosylceramide synthase (GCS) that catalyzes the first committed step of GSL biosynthesis, thereby reducing the rate of synthesis of Gb3 to a level compatible with its residual clearance. The expected result is a reduction of net Gb3 load in tissues resulting in symptomatic improvement and a delayed progression towards end-stage organ failure.

1.2.2 Nonclinical summary

Nonclinical pharmacology studies were performed in mice. Pharmacokinetic (PK), metabolism, and toxicology *in vitro* and *in vivo* studies were performed in mice, rats, rabbits and dogs.

In summary, lucerastat dose dependently inhibits GCS at low micromolar concentrations, and reduces Gb3 storage and lysosomal staining in cultured FD subject fibroblasts, including fibroblasts from subjects with mutations associated with very low or no residual α -GalA activity [Welford 2017, Welford 2018]. In a mouse model of FD devoid of α -GalA activity oral lucerastat reduces Gb3 levels in the dorsal root ganglia (DRG) and in the kidney. In other mouse models of related GSL storage disorders such as Sandhoff disease, and GM1 gangliosidosis, lucerastat prolongs life span and improves clinical manifestations.

In rats and dogs, hepatic elimination is negligible and the main route of elimination is renal excretion of unchanged lucerastat. *In vitro* studies showed that lucerastat is a substrate of organic cation transporter 2 (OCT2), but not of other kidney transporters. This observation triggered a clinical drug-drug interaction (DDI) study with the OCT2 inhibitor cimetidine in healthy male subjects [see Section 1.2.3].

Dermal findings of low severity were present in rats and dogs. They consisted of acanthosis (epidermal hyperplasia), along with hyperkeratosis and lymphoid cell infiltration, in rats at doses ≥ 1000 mg/kg/day given for 26 weeks and in dogs at doses ≥ 300 mg/kg/day given for up to 39 weeks. The changes were mild, reversible, without further consequences, and thus considered not adverse. As skin findings were observed both in rodents and in non-rodents, and these findings might be related to exaggerated pharmacodynamic (PD) effects, it is recommended that the skin be monitored in clinical studies.

Embryo-fetal toxicity studies indicated that lucerastat has embryotoxic potential in rats and rabbits and teratogenic potential in rabbits at high doses inducing maternal toxicity.

In rat fertility studies, lucerastat had no effects on female fertility, while male fertility was reduced at doses ≥ 500 mg/kg/day. The 26-week toxicity study in rats showed changes in sperm parameters and microscopic findings in the testes and epididymides. In CD-1 mice and dogs, no changes in sperm parameters (assessed in the 13-week mouse study and the 4-week dog study) were seen. In addition, no histopathological effects in the testes were seen when lucerastat was administered for up to 13 weeks in mice and 39 weeks in dogs. Systemic exposure levels reached in mice and dogs were similar to or higher than those producing effects on the male reproductive system of rats. In the absence of changes in sperm parameters and microscopic findings in dogs and mice, the testicular toxicity observed in rats is considered unlikely to be relevant in man.

More detailed information can be found in the Investigator's Brochure (IB) [[Lucerastat IB](#)].

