### **10.2 Laboratory data**

- Change from baseline to each visit up to Month 6;
- Treatment-emergent marked abnormalities;

Laboratory analyses are based on data received from the central laboratory as well as local laboratories. The laboratory parameters considered as safety parameters are the following:

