### Male reproductive hormones (local protocol)

- Total testosterone (nmol/L);
- Free testosterone (pmol/L);
- Follicle-stimulating hormone (IU/L);
- Luteinizing hormone (IU/L);
- Inhibin B (ng/L).

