## 16.2 Laboratory data

### 16.2.1 Change from baseline to each visit up to Month 6

For quantitative parameters, summaries of the observed value and change from baseline at each visit will be presented by treatment group, using the windowed times as described in [Table 15](#). For categorical parameters (e.g., proteinuria), shift tables reflecting change from baseline will be presented by treatment group at each visit, using the windowed times as described in [Table 15](#). Results of male reproductive hormones and of semen analyses will be listed.

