**Table 18**      **Marked abnormalities for urinalysis (dipstick analysis)**

Variable	Abnormality
Bilirubin	3+ (HH flag)
Occult blood	3+ (HH flag)
Glucose	3+ (HH flag)
Ketones	3+ (HH flag)
Leukocyte esterase	3+ (HH flag)
Protein	3+ (HH flag)

Patient listings will also flag values without marked abnormalities but outside of the normal range as H (high; LB.LBNRIND = HIGH) or L (low; LB.LBNRIND = LOW). Results with LB.LBSTRESC available as < x.x (below x.x) will be displayed as < x.x in the patient listing but analyzed as x.x (equal to x.x). Results with LB.LBSTRESC available as > x.x (above x.x) will be displayed as > x.x in the patient listing but analyzed as x.x (equal to x.x).

Semen analysis data will be listed with a flag (L) for sperm concentrations corresponding to a decrease from baseline of 50% or more.

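### Male hormone and semen results are named as safety parameters but only listed, so a fall in sperm concentration cannot be set against the placebo men or quantified

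*Protocol*

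**What the plan says.** Protocol 1.2.2 states that in rats "male fertility was reduced at doses ≥ 500 mg/kg/day" and that "The 26-week toxicity study in rats showed changes in sperm parameters and microscopic findings in the testes and epididymides". The same section gives the other side. Sperm parameters did not change in a 13-week mouse study or a 4-week dog study, and testicular histology was clean up to 13 weeks in mice and 39 weeks in dogs. It adds that "Systemic exposure levels reached in mice and dogs were similar to or higher than those producing effects on the male reproductive system of rats" and concludes that "the testicular toxicity observed in rats is considered unlikely to be relevant in man".

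SAP 10.2 sets two laboratory endpoints: change from baseline to each visit, and treatment-emergent marked abnormalities. It then says "The laboratory parameters considered as safety parameters are the following". The list includes total and free testosterone, FSH, LH and inhibin B, followed by sperm concentration, ejaculate volume, total sperm number (which the SAP derives), motility and the percentage of normal sperm.

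SAP 16.2.1 gives quantitative laboratory parameters summaries of value and change by treatment group at each visit, then makes an exception: "Results of male reproductive hormones and of semen analyses will be listed". SAP 16.2.2 tabulates marked abnormalities by treatment group for the parameters in Tables 16 to 18. Below Table 18 it adds: "Semen analysis data will be listed with a flag (L) for sperm concentrations corresponding to a decrease from baseline of 50% or more".

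**The concern.** Neither endpoint in SAP 10.2 receives an analysis by arm for these ten variables, and the SAP gives no reason. Sperm concentration varies from sample to sample within a man, so a flagged fall has no clear meaning unless the rate in the placebo men stands beside it. A moderate shift across the lucerastat group would leave most men unflagged, and a shift in motility, normal forms, total sperm number or a hormone would raise no flag at all. Randomized, placebo-controlled data on a body system with a reported animal finding would be collected but not put into a form that supports a statement about treatment.

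**Working it through.** **1. Text against text.**

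| Item | Other quantitative laboratory parameters | Hormones and semen |
|---|---|---|
| Safety parameter in SAP 10.2 | yes | yes |
| Value and change by arm (SAP 16.2.1) | yes | no, listed |
| Marked abnormality by arm (SAP 16.2.2) | those in Tables 16 to 18 | none appears in Tables 16 to 18 |
| Listing flag | yes | sperm concentration only, fall of 50% or more |

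The documents give no number of men, sampling schedule or precision for these data, so there is no plan figure to reproduce. Steps 2 to 4 rest on assumed SDs and numbers.

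**2. Chance rate of the flag.** Let s be the within-man SD of log concentration. The log change between two samples then has SD s√2. With a normal log change and no treatment effect, P(flag) = Φ(ln 0.5 / (s√2)), where ln 0.5 = −0.693.

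- s = 0.3: Φ(−0.693/0.424) = Φ(−1.63) = 5.1%
- s = 0.4: Φ(−0.693/0.566) = Φ(−1.23) = 11.0%
- s = 0.5: Φ(−0.693/0.707) = Φ(−0.98) = 16.3%

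These are rates per post-baseline sample, in either arm. With an assumed 20 lucerastat men, 20 × 0.051 = 1.0 to 20 × 0.163 = 3.3 flags are expected by chance at each sample.

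**3. Sensitivity of the flag to a group shift.** Suppose every lucerastat man has a true fall of 30% (ln 0.7 = −0.357). Then P(flag) = Φ((−0.693 + 0.357)/(s√2)).

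- s = 0.3: Φ(−0.79) = 21%
- s = 0.5: Φ(−0.48) = 32%

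So 68% to 79% of men with such a fall are unflagged at a given sample. The rise from 5% to 21%, or from 16% to 32%, can be recognised only against a placebo rate.

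**4. What an estimate by arm would give.** The 95% CI for the lucerastat/placebo ratio of change in concentration has factor exp(t × SD × √(1/n₁ + 1/n₀)), where SD is that of the log change, here assumed to be 0.5 to 1.0. At 20 vs 10 and SD 0.5: exp(2.048 × 0.5 × 0.387) = exp(0.397) = 1.49. The last column is 1 − 1/factor, the fall beyond which an observed ratio of exactly 1 would exclude.

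| Men (lucerastat vs placebo) | Factor at SD 0.5 / 0.8 / 1.0 | Fall excluded beyond |
|---|---|---|
| 8 vs 4 | 1.98 / 2.98 / 3.91 | 49% / 66% / 74% |
| 20 vs 10 | 1.49 / 1.89 / 2.21 | 33% / 47% / 55% |
| 40 vs 20 | 1.32 / 1.55 / 1.73 | 24% / 35% / 42% |

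With 12 men a halving is at the edge of exclusion at SD 0.5 and not excluded at the larger SDs. With 30 to 60 men and SD 0.5 to 0.8 it is excluded if the observed ratio is near 1.

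**5. The zero problem.** SAP section 14 sets percent change to missing when baseline is above zero and the post-baseline value is zero. A geometric-mean percent change taken over unaltered would therefore drop a man whose count falls to zero, which is the worst outcome.

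**The case against.** Much of the other side stands.

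- A reader might infer that a testicular effect could not be seen. That is too strong: every result is listed, and large falls in concentration are flagged. If the true flag rate were 20%, the chance of at least one flagged man among 20 on lucerastat would be 1 − 0.8²⁰ = 99%.
- A reader might infer that analysis by arm would exclude such an effect. That depends on a number of men the documents do not give, and with about 12 men it would probably not.
- A reader might infer that these data were collected to follow up the rat finding. No section says so, and Protocol 1.2.2 gives reasons for discounting that finding. Its negative sperm data come from studies shorter than both the 26-week rat study and the 6-month treatment period, but the dog histology runs to 39 weeks.
- The local-protocol label stands on the hormone heading only. That semen sampling is also local is inferred from its absence from Protocol 7.2.4.2. Local protocol 5.VHP.B was not available and may set its own schedule or rules.
- The SAP breaks no promise in the global protocol. Protocol 10.3.5.4.1 covers hematology, blood chemistry, cardiac enzyme and urinalysis, and Protocol 10.3.5 puts all safety data in listings.

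These points limit the claim but do not close the gap. SAP section 1 says the SAP is based on that local protocol too and covers all safety endpoints, so the tables belong here.

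**Conclusion.** The point holds in a limited form. SAP 10.2 names these variables as safety parameters with change from baseline and marked abnormalities as endpoints. SAP 16.2.1 and 16.2.2 then plan only listings, with one flag on one variable. Individual or gross falls remain visible. What is missing is any count or estimate by arm, so a fall can be neither compared with the placebo rate nor quantified.

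The size rests on assumptions. Chance flags run at about 5% to 16% per sample if the within-man SD of log concentration is 0.3 to 0.5, and the gain in precision depends on an unknown number of men. The documents do not support the stronger reading that a testicular effect could be neither seen nor excluded. No primary, secondary or multiplicity-controlled conclusion is affected. This is a worthwhile, inexpensive improvement to safety reporting.

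**What to change.** In SAP 16.2.1 and 16.2.2, keep the listing and add descriptive summaries by arm, without formal tests and with the number of men per arm stated:

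- Observed value and change from baseline for every semen and hormone variable, using absolute change for motility and normal forms, which are percentages.
- Ratio to baseline with 95% CI for sperm concentration, total sperm number and the hormones. State a rule that keeps post-baseline zeros in the analysis instead of setting them to missing as in section 14, for example a rank-based or median summary, or a substituted lower limit.
- Number and percentage of men at risk with a fall of 50% or more in sperm concentration, counting falls to zero.

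The cost is a SAP wording change and a few tables on data already collected. The numbers may be small and the intervals wide, and a halving may not be excluded, so the output should be labelled descriptive.

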1.2.3 Clinical summary

A total of six Phase 1 studies have been completed, which overall enrolled 180 subjects: one single-ascending dose study (n = 39) and one multiple-ascending dose study (n = 37) in healthy male subjects, one study in subjects with different degrees of renal function impairment (n = 32), one exploratory Phase 1b study in subjects with FD (n = 14), one DDI study in healthy male subjects (n = 14), and one thorough QT (TQT) study in healthy subjects (n = 44). In the DDI study, lucerastat was administered concomitantly with the OCT2 inhibitor cimetidine at steady state.

Across the six Phase 1 studies, lucerastat has been administered to 152 subjects including 10 subjects with FD. It was found to be safe and well tolerated at all dose regimes evaluated (single oral doses up to 4000 mg, repeated oral doses up to 1000 mg twice daily [b.i.d.] for 12 weeks [on top of ERT], and a single oral dose of 500 mg administered concomitantly with cimetidine at steady state).

Overall, in the completed studies, there were 2 serious AEs (SAEs): One SAE of recurrent femoral thrombosis was reported in a subject with severe renal function impairment, and medical history of factor V Leiden gene mutation. Another SAE of re-occurrence of atrial fibrillation in the context of hypertrophic cardiomyopathy was reported in a subject with FD with a history of transient ischemic attack and atrial fibrillation.

Among other AEs, there was one with alanine aminotransferase (ALT) $5 \times$ upper limit of normal (ULN) and aspartate aminotransferase (AST) $2.5 \times$ ULN in a healthy subject leading to study drug discontinuation and full resolution thereafter. Total bilirubin remained within normal range. Few subjects in both lucerastat and placebo groups reported medically irrelevant AEs of increased liver enzymes.

After single dosing of lucerastat (range: 100–4000 mg) in healthy subjects, peak plasma drug concentrations were attained between 0.5 and 4.0 h, and the apparent terminal elimination half-life ($t_{1/2}$) ranged from 3.6–16.9 h. Following repeated administration of lucerastat (range: 200–1000 mg b.i.d.), peak plasma concentration observed during the dosing interval were attained between 0.5 h and 4.0 h. The PK of lucerastat were proportional for the area under the plasma concentration-time curve (AUC) extrapolated to infinity ($AUC_{0-\infty}$) over the dose range tested after both single and multiple dosing. There was no relevant increase in exposure from Day 1 to Day 7, indicating absence of accumulation over time. The time to reach steady state was approximately 2 days.

Renal clearance of unchanged lucerastat varied from 68–85% of oral clearance and mean renal excretion of unchanged lucerastat per daily dose from 68–85%. No clinically relevant food effect was observed.

The PK results of 1000 mg b.i.d. obtained in subjects with FD were in line with those observed in healthy subjects. The PK profiles of lucerastat were similar in subjects with

mild renal function impairment when compared with healthy subjects. Plasma lucerastat concentrations were higher in subjects with moderate and severe renal function impairment. The $t_{1/2}$ was longer in subjects with moderate (9.6 h) or severe renal function impairment (16.1 h) than in healthy subjects (7.0 h). Overall, this resulted in a 1.6- and 3.2-fold increase in $AUC_{0-\infty}$ of lucerastat in subjects with moderate and severe renal function impairment, respectively, when compared with healthy subjects.

In the DDI study with the OCT2 inhibitor cimetidine, 14 healthy male subjects received a single oral dose of 500 mg lucerastat (on Day 1), as well as a single oral dose of 500 mg lucerastat (on Day 6) administered concomitantly with cimetidine at steady state (multiple oral doses of 800 mg b.i.d. cimetidine from Day 3 to Day 9). Results from the DDI study demonstrated that cimetidine had only a weak effect on the exposure to lucerastat, i.e., the geometric mean (90% confidence interval [CI]) $AUC_{0-\infty}$ increased by 22% (16%; 27%) when lucerastat was administered concomitantly with cimetidine at steady state, as compared to lucerastat alone. Geometric mean (90% CI) maximum observed plasma concentration (C_{max}) was almost unchanged (i.e., increased by 4% [8%; 17%]) and absorption was slower (i.e., time to reach C_{max} [t_{max}] delayed by 1 h). Geometric mean $t_{1/2}$ was not changed. These effects are considered as not clinically relevant. Based on this, lucerastat can be administered concomitantly with OCT2 inhibitors without need for dose adaptation.

The TQT study was split into two parts: Part A was a double-blind, placebo-controlled study in healthy male subjects to determine the suprathreshold dose of lucerastat to be used in Part B. Part B was a randomized, double-blind (for lucerastat), placebo-controlled, four-way crossover study including an open-label positive control in healthy male and female subjects to assess the effect of single therapeutic and suprathreshold doses of lucerastat on the QT/QTc interval duration. In Part A, 6 subjects received a single oral dose of 2000 mg lucerastat on Day 1 and a single oral dose of 4000 mg lucerastat on Day 3, whereas 2 subjects received placebo both on Days 1 and 3. In Part B, 36 subjects were enrolled. Subjects received, in a random sequence, single oral doses of 1000 mg lucerastat (anticipated therapeutic dose), 4000 mg lucerastat (suprathreshold dose), 400 mg open-label moxifloxacin (positive control to assess assay sensitivity), and placebo. Based on concentration-QTc analysis, a QTc according to Fridericia's formula (QTcF) effect of clinical concern (i.e., above 10 ms) could be excluded up to lucerastat plasma concentrations of approximately 34 $\mu\text{g/mL}$. The results constituted a negative TQT study, demonstrating that lucerastat up to a single dose of 4000 mg does not have any clinically relevant liability to prolong the QT interval or any clinically relevant effect on other ECG parameters.

In the exploratory Phase 1b study, a marked change in biomarkers was observed in subjects with FD who received 1000 mg b.i.d. lucerastat on top of ERT, with a mean percentage change from baseline (standard deviation [SD]) of -49% (17), -33% (13), and -55% (10)

in plasma levels of glucosylceramide (GlcCer), lactosylceramide (LacCer), and Gb3, respectively, at Week 12.

Urinary Gb3 was also decreased by 53% (21) at Week 12.

There was no change in plasma GlcCer, LacCer or Gb3 in the control group. No significant changes were observed for plasma lysoGb3 in either group. The concomitant decrease in GlcCer, LacCer, and Gb3 confirms GCS inhibition and α -GalA substrate reduction with lucerastat in subjects with FD.

More detailed information can be found in the IB [[Lucerastat IB](#)].

